#### **6.4.1.3. Consent for Pharmacogenomics Assessment (optional)**

Participation in the pharmacogenomics portion of the trial is optional and requires separate informed consent. Participation in the pharmacogenomics portion of the trial will not affect participation in the trial. Subjects may withdraw consent from pharmacogenomics portion of the trial without withdrawing from the trial.

Specimens that may be used for pharmacogenomics testing include: blood and tumor specimens collected during this trial.

The investigator or qualified designee will explain the optional pharmacogenomics assessment portion of the consent to the subject, answer all of his/her questions, and obtain written informed consent before performing any procedure related to pharmacogenomics assessment. A copy of the informed consent will be given to the subject.

#### **6.4.1.4. Review of Inclusion and Exclusion Criteria**

All inclusion and exclusion criteria will be reviewed by the investigator or qualified designee to ensure that the subject qualifies for the trial.

#### **6.4.1.5. Emergency Medical Support and Subject Card**

All subjects will be given an Emergency Medical Support and Subject Card identifying them as participants in a research trial. The card will contain trial site contact information (including direct telephone numbers) to be utilized in the event of an emergency. The investigator or qualified designee will provide the subject with an Emergency Medical Support and Subject Card immediately after the subject provides written informed consent.

#### **6.4.1.6. Medical History**

A medical history will be obtained by the investigator or qualified designee. Medical history will include all active conditions; history of hepatitis B virus (HBV), hepatitis C virus (HCV), HIV and/or HPV; and any condition diagnosed within the prior 10 years that are considered to be clinically significant by the Investigator. Medical history will also include an assessment of smoking history.

History of the cancer under study will be recorded *separately* (see Section 6.4.1.9); all other cancer history should be captured in the medical history.

For subjects in Phase 2, in addition, record any prior cancer other than cervical cancer even if diagnosed greater than 10 years prior to Visit 1.

#### **6.4.1.7. Review of Baseline Symptoms**

Baseline symptoms associated with the disease under study will be assessed for each subject at screening. Baseline symptoms will be Graded and recorded according to NCI CTCAE Version 4.03. Baseline symptoms will be characterized in terms including seriousness, causality to previous treatment, toxicity grading, and action(s) taken if any.

#### **6.4.1.8. Review of Prior and Concomitant Medications**

##### ***6.4.1.8.1. Prior Medications***

All medication — other than chemotherapy — taken by the subject within 30 days before starting the trial will be recorded. In addition, all treatments for a prior cancer other than current cancer will be recorded, even if taken greater than 30 days prior to Visit 1.

Prior treatments for the current cancer will be recorded *separately* (see Section 6.4.1.9) and not listed as a prior medication.

##### ***6.4.1.8.2. Concomitant Medications***

Any medication taken by the subject during the trial, from the date of consent through the 30-day Safety Follow-up Visit, will be recorded. After the Safety Follow-up Visit, record all medications related to reportable SAEs and AESIs as defined in [Section 7.2.2.2](#).

#### **6.4.1.9. Cancer Disease Details and Prior Treatment**

Obtain current cancer disease details and prior treatment for all subjects including:

- Detailed history of the tumor at diagnosis *and* study entry including histopathological diagnosis, grading, and staging in accordance with the AJCC-8 Tumor Node Metastasis (TNM) classification ([Amin et al 2017](#)).
- All therapy used for prior treatment of the disease under study (including but not limited to surgery, radiotherapy [including total radiation dose received and general treatment field], and any systemic treatment) — and for each therapy, complete dosing schedule and their corresponding best response.
- Any other conditions treated with radiation therapy or and any systemic treatment.

- Current cancer signs and symptoms, and side effects from current and/or previous anticancer treatments.
- Current cancer disease status.
- Relevant somatic or germline mutations detected.
- Chronic viral infection status, if available.
- Human epidermal growth factor receptor 2 (HER2) status, if available.
- Smoking history.
- Tumor markers, including but not limited to, molecular/genetic or immunohistochemistry markers (such as PSA, CA125, AFP, *BRCA*, PD-L1 status, etc.), if applicable and available.
- HPV status, if available.

#### **6.4.1.9.1. Subsequent Antineoplastic Therapy**

The investigator or qualified designee will review all new antineoplastic therapy initiated after the last dose of study drug. If a subject initiates a new antineoplastic therapy within 4 weeks after the last dose of study drug, the Safety Follow-up Visit must occur before the first dose of the new therapy.

Subjects in Phase 2 will move into survival follow-up once new antineoplastic therapy has been initiated.

#### **6.4.1.9.2. Survival Follow-up (Phase 2 only)**

Once a subject in Phase 2 moves into the survival follow-up period, they should be contacted by telephone every 2 months for up to 12 months after their last dose of study drug. (See also [Section 6.3.4.2.](#))

#### **6.4.1.10. Assignment of Subject Trial Number**

After a subject signs an informed consent form, the subject will be assigned a unique, sequential subject number. Once a number is assigned, it cannot be reassigned if the original subject is found to be ineligible or withdraws consent.

#### **6.4.1.11. Trial Compliance**

Any delay from the protocol-specified AGEN2034 dosing frequency which is due to toxicity and which results in > 6 weeks between AGEN2034 doses requires consultation between the investigator and the Sponsor, and written documentation of the collaborative decision on subject management.

Administration of trial medication will be witnessed by the investigator and/or trial staff. The total volume of trial treatment infused will be compared to the total volume prepared to determine compliance with each dose administered.

Any reason for noncompliance should be documented. Noncompliance is defined as a subject missing >1 cycle of study treatment *for non-medical reasons*. If 1 cycle was missed and the

interval between the subsequent treatment cycle and the last administered treatment cycle is longer than 4 weeks for non-medical reasons, criteria for insufficient compliance are met.

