#### **4.4. Criteria for Subject Withdrawal**

##### **4.4.1. Withdrawal from Treatment**

The subject must be withdrawn in the event of any of the following:

- Occurrence of an event that would have been considered an exclusion criterion prior to enrollment, that is clinically relevant and affects the subject's safety, and if discontinuation is considered necessary by the investigator and/or Sponsor.
- Radiological disease progression, defined by RECIST 1.1 as defined in [Section 6.4.4.3](#), unless the subject is considered to derive clinical benefit from the treatment by the investigator, is clinically stable and there is agreement with the Sponsor ([Section 5.4.5](#)).

Clinical stability is defined by:

- Absence of new symptoms and signs indicating clinically significant disease progression
- No decline in ECOG performance status.
- Absence of rapid progression of disease or progressive tumor at critical anatomical sites (e.g., cord compression) requiring urgent alternative medical intervention.

- Note: For Phase 2, tumor assessments should be performed every 6 weeks ( $\pm$  3 days) from first treatment dose until discontinuation of treatment, regardless of reason for discontinuation. This includes patients who are being treated past disease progression. Clinical disease progression, in the absence of radiologic progression on the basis of RECIST 1.1, including 1 or more of the following:
  - signs and/or symptoms of consistent with clinically significant progression of disease, including worsening of laboratory values, appearance of new lesion/worsening of the lesion best seen clinically, etc.
  - decline in ECOG performance status
  - tumor progression at critical anatomical sites that requires urgent medical intervention (e.g., CNS metastasis with potential for cord progression)
  - initiation of chronic opiates, or initiation of chemotherapy or new antineoplastic therapy, palliative radiation therapy, or surgery
- Any Grade 2 drug-related uveitis or eye pain or blurred vision that does not respond to topical therapy and does not improve to Grade 1 severity within 2 weeks OR requires systemic treatment;
- Any Grade  $\geq$  2 drug-related pneumonitis or interstitial lung disease that does not resolve to dose delay and systemic corticosteroids (also see Pulmonary Immune Related Adverse Event Management Algorithm [[Section 5.6.3](#)]);
- Any Grade 2 or 3 drug-related toxicity that does not resolve in  $\leq$  6 weeks;

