- Any Grade 3 drug-related bronchospasm, hypersensitivity reaction, or infusion-related reaction, regardless of duration; with the exception of Grade 3 infusion-related reactions resolving within 6 hours and controlled with medical management;
- Any Grade 3 non-skin, drug-related AE lasting  $>$  7 days, with the following exceptions for uveitis, pneumonitis, bronchospasm, diarrhea, colitis, neurologic toxicity, hypersensitivity reactions, infusion reactions, endocrinopathies, and laboratory abnormalities:
  - Grade 3 drug-related uveitis, pneumonitis, bronchospasm, diarrhea, colitis, neurologic toxicity, hypersensitivity reaction, or infusion reaction of any duration requires discontinuation;
  - Grade 3 drug-related endocrinopathies adequately controlled with only physiologic hormone replacement do not require discontinuation;
  - Grade 3 drug-related laboratory abnormalities do not require treatment discontinuation except:
    - Grade 3 drug-related thrombocytopenia  $>$  7 days or associated with bleeding requires discontinuation;
    - Any drug-related liver function test (LFT) abnormality that meets the following criteria require discontinuation (also see hepatic immune-related AE management algorithm [[Table 7](#)]):

- ▶ AST or ALT  $> 8 \times$  ULN;
- ▶ Total bilirubin  $> 5 \times$  ULN;
- ▶ Concurrent AST or ALT  $> 3 \times$  ULN AND total bilirubin  $> 2 \times$  ULN;
- Any Grade 4 drug-related AE or laboratory abnormality, except for the following events, which do not require discontinuation:
  - Grade 4 neutropenia  $< 7$  days;
  - Grade 4 lymphopenia or leukopenia;
  - Isolated Grade 4 electrolyte imbalances/abnormalities that are not associated with clinical sequelae and are corrected with supplementation/appropriate management within 72 hours after their onset;
- Any AE, laboratory abnormality, or intercurrent illness which, in the judgment of the Investigator, presents a substantial clinical risk to the subject with continued treatment;
- Tumor flare phenomenon, defined as local pain, irritation, or rash localized at sites of known or suspected tumor does not require treatment discontinuation.
- Any requirement for  $\geq 10$  mg per day of prednisone (or equivalent) for  $> 6$  weeks;
- Any recurrence of a Grade 3 or 4 drug-related toxicity;
- Dose delay which results in no AGEN2034 dosing for more than 6 weeks.

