- Occurrence of AEs, resulting in discontinuation of trial drug that is desired or considered necessary by the investigator and/or the subject (if applicable).
- Occurrence of pregnancy (if applicable).
- Use of a non-permitted concomitant drug, as defined in [Section 5.5.2](#), in which the predefined consequence is withdrawal from study drug (Sponsor may be contacted to discuss whether trial treatment must be discontinued).
- Noncompliance for non-medical reasons ([Section 6.4.1.11](#))

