**Table 2: Phase 1 Dosing Regimens**

Part and Agent	Dose	Schedule	Duration of Treatment
Part A1: Dose Level 1			
AGEN2034	1 mg/kg IV 	Every 2 weeks	Up to 24 months
Part A1: Dose Level 2			
AGEN2034	3 mg/kg IV 	Every 2 weeks	Up to 24 months
Part A1: Dose Level 3			
AGEN2034	10 mg/kg IV 	Every 2 weeks	Up to 24 months
Part A2: Dose Level 1			
AGEN2034	6 mg/kg IV 	Every 3 weeks	Up to 24 months
Part A2: Dose Level 2			
AGEN2034	10 mg/kg IV 	Every 3 weeks	Up to 24 months

 Infusion time is 60 minutes (-10/+20 min)

In Phase 2, all subjects will receive AGEN2034 at a dose of 3 mg/kg IV over 60 minutes (-10/+20 min) every 2 weeks for up to 24 months.

In both Phases, subjects will be treated for up to 24 months, regardless of dose delays, as long as the subject meets criteria to remain on therapy.

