### 5.4.4.2. Treatment Delay

#### 5.4.4.2.1. *Criteria for Treatment Delay*

AGEN2034 administration should be delayed for the following:

- Any Grade  $\geq 2$  non-skin, drug-related AE with the following exceptions:
  - Do not delay treatment for Grade  $\geq 2$  Fatigue and laboratory abnormalities except for:
    - Delay dosing for Grade  $\geq 2$  serum creatinine (more than 1.5x baseline) toxicity
    - If a subject has a baseline AST, ALT, or total bilirubin that is within normal limits, delay dosing for drug-related Grade  $\geq 2$  toxicity;
- Any Grade  $\geq 3$  skin drug-related AE or suspected Stevens-Johnson syndrome (SJS) or toxic epidermal necrolysis (TEN)
- Any Grade  $\geq 3$  drug-related laboratory abnormality with the following exceptions for lymphopenia, AST, ALT, or total bilirubin:
  - Grade 3 lymphopenia does not require a dose delay.
  - If a subject has a baseline AST, ALT, or total bilirubin that is within normal limits, delay dosing for drug-related Grade  $\geq 2$  toxicity.
  - If a subject has baseline AST, ALT, or total bilirubin within the Grade 1 toxicity range, delay dosing for drug-related Grade  $\geq 3$  toxicity.
- Any AE, laboratory abnormality, or inter-current illness which, in the judgment of the investigator, warrants delaying the dose of study drug.

Subjects receiving AGEN2034 who have drug-related toxicities that meet the criteria for dose delay should have treatment delayed until retreatment criteria are met.

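### For a toxicity-related gap of more than 6 weeks between doses, Protocol 4.4.1 requires withdrawal from treatment, while 6.4.1.11 asks only for consultation and a documented decision

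*Protocol*

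**What the plan says.** Protocol 4.4.1 (Withdrawal from Treatment) opens its list with "The subject must be withdrawn in the event of any of the following". One entry is "Dose delay which results in no AGEN2034 dosing for more than 6 weeks". It names no cause, no exception and no role for the Sponsor.

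Protocol 6.4.1.11 (Trial Compliance) addresses "Any delay from the protocol-specified AGEN2034 dosing frequency which is due to toxicity" and says that such a delay "which results in > 6 weeks between AGEN2034 doses requires consultation between the investigator and the Sponsor". The stated output is "written documentation of the collaborative decision on subject management". The section does not mention mandatory withdrawal and does not point to the dose-delay entry in 4.4.1.

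Two other places deal with delays. Protocol 5.4.4.2.1 says that subjects meeting the delay criteria "should have treatment delayed until retreatment criteria are met". Protocol 5.4.1.1, in the text below Table 2, says that "subjects will be treated for up to 24 months, regardless of dose delays, as long as the subject meets criteria to remain on therapy".

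**The concern.** Two instructions start from the same threshold and end differently: one removes the subject from treatment, the other leaves the outcome to a case-by-case decision in which the Sponsor takes part. Sites will meet both, because the noncompliance entry in 4.4.1 itself refers the reader to 6.4.1.11.

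Two sites could handle identical subjects differently and each could cite the protocol. In an open-label, single-arm trial that inconsistency goes straight into the safety tables: who counts as discontinued and why, how long subjects were exposed, and how long adverse events count as treatment-emergent. It also leaves open whether a retained subject has a protocol deviation.

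**Working it through.** The plan gives no figure on this point to reproduce, so the check is a comparison of the texts, followed by simple date arithmetic for one affected subject.

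**1. Is the trigger the same?** For toxicity, yes. Both sections use more than 6 weeks without AGEN2034. Section 4.4.1 covers delays of any cause and 6.4.1.11 only those due to toxicity, so every case under 6.4.1.11 is also a case under 4.4.1.

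**2. Is the consequence the same?** No.

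| | 4.4.1 | 6.4.1.11 |
|---|---|---|
| Cause | Any | Toxicity |
| Threshold | More than 6 weeks | More than 6 weeks |
| Consequence | Withdrawal from treatment, mandatory | Consultation and a documented decision |

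**3. Is discretion implied in 4.4.1?** Where that section intends discretion, it says so. The radiological progression entry allows continuation with the Sponsor's agreement, and the entry on non-permitted drugs adds "Sponsor may be contacted to discuss whether trial treatment must be discontinued". The dose-delay entry has nothing similar.

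**4. Does another section settle it?** No. Sections 5.4.4.2.1 and 5.4.4.2.2 set conditions for delaying and resuming but no maximum delay. Section 5.4.1.1 refers back to the criteria for remaining on therapy, which is the point in dispute.

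**5. For whom does the conflict matter?** Other entries in 4.4.1 already withdraw many subjects with long toxicity delays: Grade 2 or 3 drug-related toxicity unresolved at 6 weeks, several Grade 3 events of any duration, most Grade 4 drug-related events, and prednisone of 10 mg/day or more for over 6 weeks. What remains is the subject who meets none of these but whose dosing gap still exceeds 6 weeks.

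The protocol's own figures show that this can happen. Table 6 (Grade 2 pneumonitis) places resumption after a steroid taper of at least 1 month, which starts once symptoms are near baseline. With the SAP 7.2 conversion (30.4375 days per month), 42 − 30.4 = 11.6 days. If more than about 11.6 days pass between the last dose and the start of the taper, the gap exceeds 42 days even though the symptoms settled well within 6 weeks.

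**6. What changes for one such subject?** Let the last dose before the gap be on day L. A gap of more than 42 days puts any next dose at L + 43 or later.

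| Quantity | Withdrawn | Redosed (minimum) |
|---|---|---|
| Last dose | L | L + 43 |
| End of on-treatment period (SAP 5.3, 35 days) | L + 35 | L + 43 + 35 = L + 78 |
| End of extended period (SAP 5.4, 90 days) | L + 90 | L + 43 + 90 = L + 133 |
| Added treatment duration (SAP 7.6.1) | – | 43 / 7 = 6.1 weeks |

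End of study would cut either window short. Protocol 8.3.4 uses 30 days instead of 35, but the shift of at least 43 days is the same.

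The choice of rule also alters discontinuation counts and reasons (SAP 7.4), events leading to permanent discontinuation, and the dose-hold and discontinuation percentages for each immune-mediated cluster (SAP 7.6.2). Deviation coding under SAP 6.2 is affected too, and through it PP EAS membership.

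**7. What does not change?** ITT EAS requires at least one dose and IERC-confirmed measurable disease at baseline. SAP Table 2 rules out exclusions based on later information, so membership of the primary efficacy set is untouched.

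**The case against.** The best defence is that 6.4.1.11 never says a subject may resume. It sits in a compliance section and states no exception to 4.4.1, so it could be an added duty to consult and document, alongside mandatory withdrawal. That reading is possible. It is strained, because an interval between doses presupposes a later dose, and a decision on management has little left to decide if withdrawal is automatic. At best the text is ambiguous on a stopping rule.

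It is also fair to say that Sponsor involvement in who stays on drug is an accepted feature elsewhere (5.4.5, treatment beyond progression), and that PP EAS is only a sensitivity set. Both points limit the importance of the conflict without removing it.

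Three stronger readings are tempting, and the documents do not support them:

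- **That every gap over 6 weeks is in conflict.** The consultation rule in 6.4.1.11 is confined to toxicity. Gaps with other causes do not meet it.
- **That tumor imaging, and so ORR, depends on the rule followed.** Section 6.4.4.1 does tie on-study imaging to drug discontinuation. But Table 13 footnote 7, which deals specifically with stopping for unacceptable toxicity, continues scans every 6 weeks until centrally determined progression. SAP 7.7.1 evaluates best overall response over all on-study assessments before new anti-cancer therapy. Any mismatch among the imaging texts is a separate matter.
- **That a number of affected subjects can be given.** Protocol 1.1.3 reports toxicity delays in 23% to 44% of nivolumab subjects, which for 150 subjects would be 0.23 × 150 = 34.5 to 0.44 × 150 = 66 with a delay of any length. The documents give neither the share of delays exceeding 6 weeks nor the share of those that escape the other 4.4.1 criteria. Any count would rest on two unsupported fractions.

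**Conclusion.** The contradiction stands, limited to toxicity-related gaps of more than 6 weeks between doses. It decides the outcome only for subjects who meet no other withdrawal criterion in 4.4.1, and their number cannot be derived from the documents. Per affected subject, the effect on last dose and on the end of both adverse-event windows is at least 43 days, assuming that the subject would be redosed under 6.4.1.11 and that end of study does not intervene. Discontinuation counts, exposure summaries and deviation coding (with PP EAS, for sensitivity only) are exposed; ITT EAS membership is not. This is an internal inconsistency that should be corrected, and no view is taken on which rule is right.

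**What to change.** Reconcile 4.4.1 and 6.4.1.11 so that one rule, chosen by the sponsor, governs toxicity-related gaps of more than 6 weeks, and cross-reference each section to the other. State whether a subject retained after consultation has a protocol deviation, so that the review under SAP 6.2 codes such subjects uniformly. The cost is protocol wording; no design, sample size or primary analysis changes.

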#### **6.4.2. Tissue Collection and Tumor Biomarker Assessment**

For Phase 2, expression of PD-L1 and HPV status will be among the exploratory biomarkers assessed in tumor samples from archival tissues or biopsies.

##### **6.4.2.1. Tissue Collection**

Tumor tissue for biomarker analysis from a biopsy of a tumor lesion not previously irradiated must be available for biomarker assessments including but not limited to PD-L1 expression and HPV evaluation. Biomarker assessment will be performed on the most recent FFPE biopsy of a tumor lesion, collected either at the time of or after the diagnosis of metastatic disease has been made, and from a site not previously irradiated. An optional tumor biopsy will be collected at Cycle 4, Day 1 (-3/+1 day) if clinically feasible to assess pharmacodynamic effects of the drug on tumor microenvironment.

- Tissue from needle or excisional biopsy or from resection is required.
- An FFPE tumor tissue block that is less than 4 years old should be provided. If an archival tumor-containing FFPE tissue block is not available, freshly cut FFPE slides (within 10 days) are acceptable for submission to the sponsor. If an FFPE tumor tissue block or freshly cut slides are not available, fresh biopsy will be required, and an FFPE tumor tissue block should be provided. If a block or freshly cut FFPE slides are not available, discuss with the study Medical Monitor prior to patient enrollment.
- Fine needle aspirates, endobronchial ultrasound (EBUS), or cell blocks are not acceptable.

If limited tissue is available, preference will be given to PD-L1 assessment.

If a tumor biopsy was obtained from a target lesion during eligibility assessment, it is preferred to obtain a new baseline scan. Biopsy of lesions on study should be limited to non-target lesions or new lesions if their pathologic etiology is ambiguous.

Tissue processing: The cancer tissues should be fixed in 10% neutral buffered formalin, paraffin embedded, and routinely processed for histological evaluation. Formalin substitutes are not suited as fixative.

